**Table 6-7: Management of Hand-Foot Syndrome (PPE) Associated with Cabozantinib**

| CTCAE v5 Grade | Action To Be Taken   |
|-----------------------|---|
| Grade 1               | Study treatment may be continued at the current dose if PPE is clinically insignificant and tolerable. Otherwise, study treatment should be reduced to the next lower dose level. a Start urea 20% cream twice daily AND clobetasol 0.05% cream once daily. Reassess at least weekly; if PPE worsens at any time or does not improve after 2 weeks, proceed to the intervention guidelines for Grade 2.                                      |
| Grade 2               | Study treatment may be continued if PPE is tolerated. Study treatment should be dose reduced or interrupted if PPE is intolerable. Continue urea 20% cream twice daily AND high potency steroid cream (eg, clobetasol 0.05%) once daily and add analgesics (eg, NSAIDs/gamma-aminobutyric acid agonists) for pain control if needed. Reassess at least weekly; if PPE worsens or affects self-care, proceed to the intervention guidelines for Grade 3. |
| Grade 3               | Interrupt study treatment until severity decreases to Grade 1 or 0. Continue treatment of skin reaction with high potency steroid cream (eg, clobetasol 0.05%) twice daily AND analgesics. Resume study treatment at a reduced dose if PPE recovers to Grade $\leq$ 1. Discontinue subject from study treatment if PPE does not improve within 6 weeks.   |

CTCAE, Common Terminology Criteria for Adverse Events; NSAID, non-steroidal anti-inflammatory drug; PPE, palmar plantar erythrodysesthesia.

a Permitted dose levels are defined by individual protocols.

### **6.7.9 Osteonecrosis**

Osteonecrosis has been reported in subjects treated with cabozantinib. Additional risk factors include use of bisphosphonates and denosumab, chemotherapy and anti-angiogenic drugs, use of corticosteroids, local radiotherapy, and dental or orofacial surgery procedures.

Osteonecrosis of the jaw (ONJ) can manifest as jaw pain, osteomyelitis, osteitis, bone erosion, tooth or periodontal infection, toothache, gingival ulceration, or gingival erosion. Persistent pain or slow healing of the mouth or jaw after dental surgery may also be manifestations of osteonecrosis.

Advise subjects regarding oral hygiene practice and to quickly report symptoms to investigator. Caution should be used in subjects receiving bisphosphonates.

Invasive dental procedures should be avoided. In cases where dental procedures are unavoidable, study treatment should be interrupted for at least 4 weeks prior to the procedure and resumed after complete wound healing has occurred. Bone healing may often require a protracted time.

### 6.7.10 Proteinuria

Proteinuria has been reported with cabozantinib. Proteinuria should be monitored by measuring UPCR. Table 6-8 provides treatment guidelines for proteinuria deemed related to study treatment.

Study treatment should be discontinued in subjects who develop nephrotic syndrome (proteinuria > 3.5 grams per day in combination with low blood protein levels, high cholesterol levels, high triglyceride levels, and edema).

**Table 6-8: Management of Proteinuria Associated with Cabozantinib**

| Severity of Proteinuria (UPCR)                       | Action To Be Taken  |
|--|---|
| ≤ 1 mg/mg
(≤ 113.1 mg/mmol)                       | 
 
No change in study treatment or monitoring
 
  |
| > 1 and < 3.5 mg/mg
(> 113.1 and < 395.9 mg/mmol) | 
 
Consider confirming with a 24-hour protein assessment within 7 days
 
No change in study treatment required if UPCR ≤ 2 mg/mg or urine protein ≤ 2 g/24 hours on 24-hour urine collection.
 
Dose reduce or interrupt study treatment if UPCR > 2 mg/mg on repeat UPCR testing or urine protein > 2 g/24 hours on 24-hour urine collection. Continue study treatment on a reduced dose if UPCR decreases to < 2 mg/mg. Consider holding study treatment if UPCR remains > 2 mg/mg despite a dose reduction until UPCR decreases to < 2 mg/mg. Restart study treatment at a reduced dose after a dose hold unless otherwise approved by sponsor.
 
Repeat UPCR within 7 days and once per week. If UPCR < 1 mg/mg on 2 consecutive readings, UPCR monitoring can revert to protocol-specific times. (Second reading is confirmatory and can be done within 1 week of first reading.) If UPCR remains > 1 mg/mg and < 2 mg/mg for 1 month or is determined to be stable (< 20% change) for 1 month, check urine protein/creatinine per protocol or as clinically indicated.
 
 |
| ≥ 3.5 mg/mg
(≥ 395.9 mg/mmol)                     | 
 
Hold study treatment pending repeat UPCR within 7 days and/or 24-hour urine protein.
 
If ≥ 3.5 on repeat UPCR, continue to hold study treatment and check UPCR every 7 days. If UPCR decreases to < 2 mg/mg, restart study treatment at a reduced dose, and monitoring of urine protein/creatinine should continue weekly until the UPCR decreases to < 1 mg/mg. If UPCR remains > 1 mg/mg and < 2 mg/mg for 1 month or is determined to be stable (< 20% change) for 1 month, check urine protein/creatinine per protocol or as clinically indicated.
 
   |
| Nephrotic syndrome                                   | 
 
Discontinue study treatment
 
   |

UPCR, urine protein creatinine ratio.

### 6.7.11 Nervous System Disorders

Cabozantinib appears to represent minimal risk of adverse neurological effects based on nonclinical Good Laboratory Practice (GLP)-compliant toxicology studies. Dysphonia, dysgeusia, headache, dizziness, confusional state, convulsion, depression, memory impairment, hypoesthesia, peripheral neuropathy, insomnia, ataxia, and encephalopathy have been observed in clinical studies with cabozantinib. The development of any new or progressive, unexplained neurological symptoms should be assessed for underlying causes.

RPLS has been reported. RPLS should be considered in any subject presenting with seizures, headache, visual disturbances, confusion or altered mental function. Study treatment should be discontinued in subjects with RPLS.

### 6.7.12 Hepatocellular Toxicity

Evaluations of aminotransferases (ALT and AST) and bilirubin have been observed during treatment with cabozantinib. It is recommended that subjects with elevation of ALT, AST, and/or bilirubin have more frequent laboratory monitoring of these parameters. If possible, hepatotoxic concomitant medications should be discontinued in subjects who develop increased values of ALT, AST, or bilirubin and other causes (eg, cancer related) should be evaluated.

**Table 6-9: Management of Hepatotoxicity Associated with Cabozantinib**

| Severity of ALT, AST, total bilirubin Elevations by CTCAE | Treatment Dose Modification   |
|---|---|
| Grade 1   | 

• Dose adjustment is usually not required.

• Consider discontinuing concomitant hepatotoxic medications and add supportive care as indicated.

   |
| Grade 2   | 

• Interrupt study treatment if lasting longer than 1 week.

• Restart study treatment after lab abnormalities have resolved to at least CTCAE Grade <math>\leq</math> 1 or baseline.

   |
| Grade $\geq$ 3  | 

• Interrupt study treatment and consider more frequent monitoring of ALT, AST, and bilirubin.

• Restart study treatment at a reduced dose after lab abnormalities have resolved to at least CTCAE Grade <math>\leq</math> 1 or baseline.

• Discontinue if lab abnormalities cannot be reversed despite interruption of study treatment.

 |

ALT, alanine aminotransferase; AST, aspartate aminotransferase; CTCAE, Common Terminology Criteria for Adverse Events

The following conditions require discontinuation of study treatment unless these laboratory abnormalities have recovered to Grade 1 or baseline level after an interruption and the sponsor has approved reinstatement of study treatment:

- Drug-related ALT or AST  $> 8 \times$  ULN.
- Drug-related ALT or AST  $> 3 \times$  ULN in combination with total bilirubin  $> 2 \times$  ULN without reasonable other explanation, consistent with drug-induced liver injury.

Elevations of aminotransferases when hepatic metastases are present may not require dose modifications if there are no progressive changes in the aminotransferases (less than a doubling) and if there are no progressive elevations in serum bilirubin concentration or coagulation factors.

#### **6.7.13 Infections and Infestations**

Infections are commonly observed in cancer subjects. Predisposing risk factors include a decreased immune status (eg, after myelosuppressive anticancer therapies, splenectomy), destructive growth of the underlying malignancy including bone marrow infiltration with suppression of normal hematopoiesis, as well as the presence of intravenous devices.

Infections and abscesses should be treated with appropriate local care and systemic therapy. Study treatment should be interrupted until adequate healing has taken place.

#### **6.7.14 Blood and Lymphatic System Disorders**

Hematological toxicities (ie, neutropenia and thrombocytopenia) and associated complications have been observed after administration of cabozantinib and may be managed with dose interruptions and/or dose reductions. Subjects with hematologic toxicities may require additional or more frequent laboratory tests according to institutional guidelines.

Dose reductions or dose interruptions for hematological toxicities are not mandated but can be applied as clinically indicated. Supportive care for thrombocytopenia or anemia, such as transfusions, may be managed according to institutional guidelines. The use of colony-stimulating growth factors should be considered. Febrile neutropenia or evidence of infection associated with neutropenia must be assessed immediately and treated appropriately and in a timely manner according to institutional guidelines.

#### **6.7.15 Fatigue**

Common causes of fatigue, such as anemia, deconditioning, emotional distress (depression and/or anxiety), poor nutrition, dehydration, sleep disturbance, and hypothyroidism should be

ruled out and treated according to standard of care. Pharmacological management should be considered after disease specific morbidities have been excluded when not prohibited.

#### **6.7.16 Weight Loss**

Anorexia and weight loss should be managed according to local standard of care including nutritional support. Pharmacologic therapy should be considered for appetite enhancement when not prohibited by a particular protocol.

#### **6.7.17 Corrected QT Prolongation**

The effect of orally administered cabozantinib 140 mg qd on QTc interval was evaluated in a placebo-controlled study in subjects with MTC. A mean increase in QTcF of 10-15 ms was observed after 4 weeks after initiating cabozantinib treatment. A concentration-QTc relationship could not be definitively established. Changes in cardiac wave form morphology or new rhythms were not observed. No cabozantinib-treated subjects in this study had a QTcF > 500 ms. Review of the larger safety database (> 15,000 subjects exposed to cabozantinib in clinical trials and in post-marketing experience) confirmed the absence of safety concerns associated with QT prolongation. There were no events of torsades de pointes reported.

Concomitant treatment with strong cytochrome P450 (CYP) 3A4 inhibitors, which may increase cabozantinib plasma concentrations, should be avoided.

If at any time on study there is an increase in QTcF to an absolute value > 500 ms, 2 additional ECGs must be performed with intervals not less than 3 min apart within 30 min after the initial ECG.

If the average QTcF from the three ECGs is  $> 500$  ms, the following actions must be taken:

- Interrupt study treatment
- Immediately notify the Sponsor and submit ECGs to the Sponsor for independent review.
- Hospitalize symptomatic subjects (eg, with palpitations, dizziness, syncope, orthostatic hypotension, a significant ventricular arrhythmia on ECG) for a thorough cardiology evaluation and management
- Consider cardiology consultation for asymptomatic subjects for evaluation and management
- Check electrolytes, especially magnesium, potassium and calcium; correct abnormalities as clinically indicated
- Check concomitant medications for any medication that may have contributed to QT prolongation, and if possible, discontinue these medications (<http://www.qtdrugs.org>)
- Repeat ECG triplicates hourly until the average QTcF is  $\leq 500$  msec, or otherwise determined by consultation with a cardiologist or appropriate expert.

Subjects with QTc prolongation and symptoms must be monitored closely until the QTc elevation and symptoms have resolved. Study treatment may be restarted at a reduced dose level if all of the following conditions are met:

- Symptoms are determined to be unrelated to the QT interval prolongation
- The QTcF value  $> 500$  ms is not confirmed
- Study treatment has been interrupted through a minimum of 1 week following the return of the QTcF to  $\leq 500$  ms.
- QT prolongation can be unequivocally associated with an event other than study treatment administration and is treatable/has been resolved
- Sponsor has reviewed all available information and has agreed to the continuation of study treatment

Following reinitiation of study treatment, ECGs must be repeated weekly for 2 weeks, then every 2 weeks for 1 month, then according to the protocol-defined time points.

Study treatment must be permanently discontinued if either of the following applies:

- Cardiac evaluation confirms that symptoms are the consequence of QT interval prolongation
- Recurrence of QTcF prolongation after reinitiation of study treatment at a reduced dose

### **6.7.18 Electrolyte Disorders**

Serum electrolyte disorders including hyponatremia, hypokalemia, hypomagnesemia, and hypophosphatemia have been reported during treatment with cabozantinib. In some cases these have been Grade 3 or 4 and/or serious. Serum electrolyte levels should be monitored frequently while receiving study treatment. Deficits should be corrected when an electrolyte abnormality is noted in order to avoid worsening. Correction of electrolyte abnormalities should be accompanied by increasing frequency of monitoring. Clinically relevant electrolyte disorders should be managed according to the dose modification guidelines as outlined in Table 6-3 or as clinically indicated. Standard clinical practice guidelines should be used for management of electrolyte disorders and may include oral or intravenous replacement.

## 7 CONCOMITANT MEDICATIONS AND THERAPIES

All concomitant medications used by the subject (including prescription and over-the-counter medications, transfusions, vitamins, herbal remedies, and nutritional supplements) during the period from 28 days before randomization through 30 days after the date of the decision to permanently discontinue study treatment are to be recorded in source documents and the CRF.

### 7.1.1 Allowed Therapies

- Antiemetics and antidiarrheal medications are allowed prophylactically according to standard clinical practice if clinically indicated.
- Granulocyte colony-stimulating factors (G-CSF or GM-CSF) are allowed if used per clinical guidelines (eg, ASCO or ESMO guidelines).
- Bisphosphonates or denosumab can be used to control bone loss or hypercalcemia if the benefit outweighs the risk per the investigator's discretion (Section 6.7.9).

Note: osteonecrosis of the jaw has been reported in subjects using bisphosphonates or denosumab. Oral examinations are recommended at screening to determine eligibility and periodically during the study. In addition, subjects should be advised regarding oral hygiene practice and to quickly report symptoms to the investigator. Frequent monitoring for potentially overlapping toxicities with study treatment is recommended.

- Transfusions and hormone replacement (including TSH-suppressive thyroid hormone therapy) should be utilized as indicated by standard clinical practice.

- Individualized anticoagulation therapy with heparin is allowed if it can be provided safely and effectively under the following circumstances:
  - *Low dose low molecular weight heparins (LMWH) for prophylactic use* are allowed if clinically indicated and the benefit outweighs the risk per the investigator's discretion.
  - *Therapeutic doses of LMWH at the time of the first dose of study treatment* are allowed if the subject has no evidence of brain metastasis, has been on a stable dose of LMWH for at least 6 weeks, and has had no complications from a thromboembolic event or the anticoagulation regimen.
  - *Therapeutic doses of LMWH after first dose of study treatment* are allowed if clinically indicated (eg, for the treatment of DVT), and the benefit outweighs the risk per the investigator's discretion. For management of thromboembolic complications while on study, refer to Section 6.7.5.
  - Accepted clinical guidelines regarding appropriate management while receiving anticoagulation therapy with heparins must be followed. This includes, but is not limited to, subject education regarding potential adverse drug reactions, monitoring laboratory parameters, dose adjustments (eg, due to kidney dysfunction).
  - For restrictions on oral anticoagulants see Section 7.1.2.

Potential drug interactions with cabozantinib are summarized in Section 7.1.2.1 and are discussed in more detail in the Investigator's Brochure.

### **7.1.2 Prohibited or Restricted Therapies**

*The following therapies are prohibited until study treatment has been permanently discontinued:*

- Any investigational agent or investigational medical device.
- Therapeutic doses of oral anticoagulants (eg, warfarin or other coumarin-related agents, direct thrombin or direct FXa inhibitors, or antiplatelet agents such as clopidogrel, or chronic use of aspirin above low dose levels for cardioprotection per local applicable guidelines).
- Any nonprotocol systemic anticancer treatment (eg, chemotherapy, immunotherapy, radionuclides, drugs or herbal products used specifically for the treatment of DTC).

*The following therapies should be avoided until study treatment has been permanently discontinued or until otherwise specified:*

- Local anticancer treatment including palliative radiation, ablation, embolization, or surgery with impact on tumor lesions should not be performed until radiographic progression per RECIST 1.1 has been established. If clinically unavoidable the investigator should consult the Sponsor prior to the procedure for safety guidance.
- Erythropoietic stimulating agents (eg, epoetin alfa and darbepoetin alfa) should not be used based on a report of increased risk of tumor recurrence/progression associated with erythropoietin (Wright et al 2007).
- Concomitant medications that are known to prolong the QTc interval should be avoided in subjects who receive cabozantinib until they have permanently discontinued cabozantinib treatment (refer to <http://www.qtdrugs.org> for a list of drugs which have the potential to prolong the QTc interval).
- Chronic co-administration of cabozantinib with strong inducers of the CYP3A4 family (eg, phenytoin, carbamazepine, rifampin, rifabutin, rifapentine, phenobarbital, and St. John's Wort) may significantly decrease cabozantinib concentrations and should be avoided. Selection of alternate concomitant medications with no or minimal CYP3A4 enzyme induction potential is recommended. See Appendix E for further details.
- Caution must be used when discontinuing treatment with a strong CYP3A4 inducer in a subject who has been concurrently receiving a stable dose of cabozantinib, as this could significantly increase the exposure to cabozantinib.
- Co-administration of cabozantinib with strong inhibitors of the CYP3A4 family (eg, boceprevir, conivaptan, posaconazole, ketoconazole, itraconazole, clarithromycin, atazanavir, indinavir, nefazodone, nelfinavir, saquinavir, ritonavir, lopinavir, telaprevir, telithromycin, and voriconazole) may increase cabozantinib concentrations and should be avoided. Grapefruit, star fruit, and Seville oranges may also increase plasma concentrations of cabozantinib and should be avoided. See Appendix E for further details.

Additional information on potential drug interactions with cabozantinib is provided in Section 7.1.2.1.

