Results from a clinical pharmacology study, XL184-007, showed that concurrent administration of cabozantinib with the strong CYP3A4 inhibitor, ketoconazole, resulted in a 38% increase in the cabozantinib exposure (AUC values) after a single dose of cabozantinib in healthy volunteers. Co-administration of cabozantinib with strong inhibitors of the CYP3A4 family (eg, boceprevir, conivaptan, posaconazole, ketoconazole, itraconazole, clarithromycin, atazanavir, indinavir, nefazodone, nelfinavir, saquinavir, ritonavir, lopinavir, telaprevir, telithromycin, and voriconazole) may increase cabozantinib concentrations. Grapefruit and Seville oranges may also increase plasma concentrations of cabozantinib. Strong CYP3A4 inhibitors and other drugs that inhibit CYP3A4 should be avoided because these drugs have the

potential to increase exposure (AUC) to cabozantinib. Selection of alternate concomitant medications with no or minimal CYP3A4 enzyme inhibition potential is recommended.

For lists of inducers and inhibitors of selected CYP450 isozyme pathways, refer to Appendix E.

Protein Binding: Cabozantinib is highly bound (approximately 99.9%) to human plasma proteins. Therefore, highly protein bound drugs should be used with caution with cabozantinib because there is a potential displacement interaction that could increase free concentrations of cabozantinib and/or a co-administered highly protein-bound drug (and a corresponding increase in pharmacologic effect). Factors that influence plasma protein binding may affect individual tolerance to cabozantinib. Therefore, concomitant medications that are highly protein bound (eg, diazepam, furosemide, dicloxacillin, and propranolol) should be used with caution. Because warfarin is a highly protein bound drug with a low therapeutic index, administration of oral anticoagulants is not allowed in subjects receiving cabozantinib due to the potential for a protein binding displacement interaction.

Other Interactions: As food increases exposure levels of cabozantinib, fasting recommendations should be followed (Section 6.1). In vitro data suggest that cabozantinib is unlikely to be a substrate for P-glycoprotein, but it does appear to have the potential to inhibit the P-glycoprotein transport activity. Additional details related to these overall conclusions can be found in the investigator brochure.

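### The on-treatment prohibited list in Protocol 7.1.2 bars oral anticoagulants only at therapeutic doses, more narrowly than the undosed bans in 7.1.2.1 and 6.7.5

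*Combined protocol and SAP*

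**What the plan says.** Section 7.1.2 opens its strict list with the words "The following therapies are prohibited until study treatment has been permanently discontinued". One bullet in that list reads "Therapeutic doses of oral anticoagulants" and gives examples: coumarin-type drugs, direct thrombin and factor Xa inhibitors, antiplatelet agents, and long-term aspirin above the low cardioprotective dose.

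Subsection 7.1.2.1, in its paragraph on protein binding, says that "administration of oral anticoagulants is not allowed in subjects receiving cabozantinib" and gives the reason as "due to the potential for a protein binding displacement interaction". The sentence begins from warfarin's high protein binding and low therapeutic index. The rule it arrives at is stated for oral anticoagulants as a class, with no dose limit.

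Section 6.7.5, on managing thromboembolic events, prefers LMWH and disallows oral anticoagulants, again without a dose limit. It puts antiplatelet agents in the same ban and makes no exception for low-dose aspirin.

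Section 7.1.1 sets out what is allowed: "Individualized anticoagulation therapy with heparin is allowed", subject to conditions. It lists "Low dose low molecular weight heparins (LMWH) for prophylactic use" separately from therapeutic doses of LMWH. It then directs the reader onward: "For restrictions on oral anticoagulants see Section 7.1.2" and "Potential drug interactions with cabozantinib are summarized in Section 7.1.2.1".

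**The concern.** A prohibited-medication list is the part of a protocol that site staff consult when a new prescription is proposed. Here the list bars less than the safety text it belongs with. The word that narrows it has a working meaning in this protocol, because 7.1.1 uses it for one kind of LMWH dosing as opposed to prophylaxis. A reader who carries that vocabulary into 7.1.2 can conclude that a prophylactic-dose oral anticoagulant is not prohibited.

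At stake is a small gap in patient protection. Section 6.7.4 notes that hemorrhage, at times fatal, has been reported with cabozantinib, so the anticoagulant rule should have one meaning wherever a site reads it. A secondary question is deviation reporting, since SAP Section 10 uses receipt of a prohibited medication as an example of a deviation code.

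**Working it through.** No arithmetic applies. The check is a comparison of every rule on oral anticoagulants.

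| Place | When it applies | Dose limit on the oral anticoagulant ban | Low-dose aspirin exception |
|---|---|---|---|
| 7.1.2, prohibited list | Until permanent discontinuation | Therapeutic doses only | Yes |
| 7.1.2.1, protein binding | While receiving cabozantinib | None | Not mentioned |
| 6.7.5 | Managing thrombotic events on study | None | No |
| 4.3, exclusion 6 | Entry | None | Yes |
| Appendix B, exclusion 6 | Crossover | None | Yes |
| 7.1.1 | On treatment, what is allowed | Not a ban; allows heparin only | Not mentioned |

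1. **Which rules overlap.** The entry and crossover criteria govern eligibility, and 6.7.5 is written for thrombotic events that have occurred. The closest comparison is therefore the 7.1.2 bullet against 7.1.2.1: the same drug class, and both in force during treatment. 7.1.2.1 speaks of subjects receiving cabozantinib, but Section 3.5.1 keeps assignment blinded, so before unblinding a site must apply it to everyone.

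2. **How they differ.** The 7.1.2 bullet covers a subset of what 7.1.2.1 covers. The difference is an oral anticoagulant below therapeutic dose, newly started on treatment.

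3. **Whether anything permits that use.** Nothing does. The only anticoagulation that 7.1.1 allows is heparin, and the only agent it names for prophylaxis is low-dose LMWH.

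4. **Whether a site could still go wrong.** It could. 7.1.1 sends the reader to 7.1.2, and the first statement there on oral anticoagulants is the qualified bullet. The full ban comes later, inside a drug-interaction subsection. A subject who would have been excluded at entry for a prophylactic-dose oral anticoagulant could start the same drug after randomization without breaching the bullet. If that subject were on placebo, the drug would then meet crossover exclusion 6 unless it was stopped.

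5. **Which wording is out of line.** Every other ban in the table is unqualified, so the 7.1.2 bullet is the exception. On aspirin, 6.7.5 is the exception: it bars antiplatelet agents outright, while the 7.1.2 bullet and both eligibility criteria allow low-dose cardioprotective aspirin.

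**The case against.** The strongest reply is that there is no contradiction. Both passages are prohibitions, one wider than the other, and giving no oral anticoagulant satisfies both. Section 7.1.2.1 is part of 7.1.2, so the pointer in 7.1.1 covers it, and 7.1.1 and 7.1.2 each also refer to 7.1.2.1 by number. Anyone who reads the whole section finds the full ban.

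This stands as far as it goes. A reader might infer that the protocol permits prophylactic oral anticoagulants, or that its rules cannot all be followed. The documents support neither reading: the apparent permission arises only from what one bullet leaves out, and nothing shows that the omission was intended. What remains is that a prohibited list should not depend on the reader finding a broader rule further on.

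A second reply is that the reason given in 7.1.2.1 is specific to warfarin and does not by itself show the same interaction risk for low-dose factor Xa or thrombin inhibitors. That is fair as to the reason. The rule itself names the class, and 6.7.5 does the same with the direct inhibitors listed.

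A third reply concerns deviations. A reader might infer that the OITT and ITT deviation summaries will be miscoded. SAP Section 10 leaves the definition of important deviations to a Protocol Deviation Management Plan that is not among the documents, and its prohibited-medication code is only an example. The same use could be coded in two ways; whether it would be cannot be checked.

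**Conclusion.** The point holds as a wording mismatch: the operative prohibited list is narrower than the protocol's own safety rule, and a site relying on the bullet alone could start a drug that 7.1.2.1 bars. It is a minor safety-consistency correction of the lowest severity.

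Its extent is one bullet and one drug class. The documents do not say how many subjects might be offered a prophylactic-dose oral anticoagulant, so no rate is claimed. The conclusion rests on reading the dose qualifier as 7.1.1 uses it for LMWH, which is natural but is not spelled out in 7.1.2.

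A reader might also wonder about efficacy. The documents give no route by which this affects the trial's conclusions. Anticoagulant use is neither a censoring event nor an intercurrent event in the PFS or ORR definitions, and sample size and alpha do not depend on it.

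**What to change.** In the 7.1.2 bullet, delete the opening three words that carry the dose qualifier, so that it bars oral anticoagulants outright as 7.1.2.1 does. Keep the existing allowance for low-dose cardioprotective aspirin, and add a reference to 7.1.1 for LMWH as the agent for prophylaxis. In 6.7.5, add the same low-dose aspirin exception to the antiplatelet wording.

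This follows the stricter rule because every other passage does. If the sponsor did mean to leave prophylactic doses open, 7.1.2.1 and 6.7.5 would have to say so instead.

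The cost is three words removed, one cross-reference and one short exception added at the next protocol amendment, with a note to sites. Subjects who need prophylaxis keep low-dose LMWH, which 7.1.1 already allows. Sample size and the analyses do not change.
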